### 2.5.1 Stratification variables for logrank tests and HRs

AI Question analysis:

- Trial (TEXT; SOFT);
- Prior/Intended chemotherapy (no; yes);
- Number of positive nodes (0; 1+).

OFS Question analysis:

- Prior chemotherapy (no;yes);
- Number of positive nodes (0; 1+), and

The analyses will **use the originally-defined strata variables**, even if the actual value on the A form has been changed within the database since the first analysis (any such changes will be **noted**).

**Since the first trial report**, it was determined that the TEXT chemo strata hadn't paid adequate attention to value of patients enrolled in PERCHE whose chemo receipt was by random assignment. Upon review, those randomized to yes-chemo were all 12/12 in the yes-chemo strata, though only 11/13 of those randomized to no-chemo were in the no-chemo strata. As above, we will use the originally-defined strata variables but the observed `adj_ct` variable now says "no chemo" for all 13 pts.

Note about the stratification of OFS Question analysis: the two methods of ovarian ablation, oophorectomy and ovarian irradiation, were planned to be grouped as the third stratification factor because few patients had specified irradiation. Even grouped, having the 3 stratification factors (for 8 strata total) resulted in some small strata sizes with sparse events especially once considering the chemotherapy cohorts separately or other subgroups and once looking at outcomes with fewer events. As such, the outcome analyses will NOT include the third stratification factor, but the endpoint analyses in the overall ITT population will be repeated with the third stratification factor included to understand ramifications of this decision.

## 2.5.2 Cohorts

The TEXT and SOFT trial populations include four cohorts of patients:

- Patients in TEXT who were randomized within 12 weeks of surgery and for whom chemotherapy was not planned;
- Patients in SOFT who did not receive chemotherapy and were randomized within 12 weeks of surgery;
- Patients in TEXT who were randomized within 12 weeks of surgery and for whom chemotherapy was planned to begin after randomization, concurrently with GnRH analogue;
- Patients in SOFT who are premenopausal after prior (neo)adjuvant chemotherapy and are randomized within 8 months of completion chemotherapy.

Therefore in addition to having trial and chemotherapy as stratification factors, it is of interest to estimate the treatment effect within cohorts of the trials' patient populations. Note, the two cohorts of TEXT and SOFT who will not receive chemotherapy may differ, considering that in TEXT all patients would receive OFS whereas in SOFT the patients may have been randomized not to receive OFS.

(n.b., We will use the chemotherapy stratification factor, which in TEXT is intended chemotherapy and therefore may be different from actual chemotherapy receipt, in a few patients).

AI Question: In addition to the overall treatment comparison, the HRs (95% CI) will be estimated within each of the 4 trial-by-chemotherapy cohorts separately. The 4 cohort HR estimates will be obtained from adding the cohort-by-treatment interaction and using contrasts to estimate HRs and CIs within each of the 4 cohorts.

The HRs (95% CI) will also be estimated by trial. To obtain these estimates, we will refit the primary Cox model with a trial-by-treatment interaction and using contrasts to estimate HRs and CIs within each of the trials.

OFS Question: In addition to the overall treatment comparison, the HRs (95% CI) will be estimated within each of the chemotherapy cohorts separately (SOFT prior chemo; SOFT no prior chemo) as described above.

## 2.6 Analysis Components

### 2.6.1 CONSORT

For the CONSORT flow diagram. Any changes (except WC/LFU) from first analysis will be noted.

Tables:

- CONSORT diagram content numbers by treatment assignment
  - Number of patients randomized
  - Number of patients included vs excluded from analysis population (noting any difference from first report)
  - Number in analysis population who never started protocol treatment (noting any difference from first report)
  - Number in analysis population who WC/LFU

- Number of patients analyzed in analysis population [same/as number included]

## 2.6.2 Follow-up compliance and WC/LFU

This section summarizes follow-up compliance, according to trial, in the ITT populations.

Tables:

- Institutional follow-up compliance group/country (rows); by trial and overall
- Withdrawn consent and lost to follow-up status

## 2.6.2 Stratification factors and patient characteristics

### 2.6.2.1 Stratification factors

Any patients for whom values of the stratification factors are determined to be different from those originally analyzed will be listed.

### 2.6.2.2 Characteristics

Because some of the values of characteristics may have changed since the first trial report, tables of characteristics of the analysis populations to be used in subgroup analyses will be re-summarized overall and by trial, cohort and treatment group. Continuous variables are summarized as mean, SD, min/max, and quartiles. Categorical variables are summarized as N(%); for variables with unavailable (missing, unknown, not done) values, the default approach is to list the number of unknowns as a category, but calculate percentages excluding these unknowns from the denominator; however there will be some variables that are frequently not assessed and in those cases the percentages will be calculated with and without the unknown category.

Table of:

- ~~Patient: age group~~
- ~~Disease: HR status, HER2 status/treatment; N status, T size, T grade~~
- ~~Treatment: local therapy (surgery/RT), chemotherapy regimen~~

## 2.6.3 Primary efficacy analysis

The primary efficacy analysis will proceed as summarized in Section 2.4 above. The data cut-off and database lock dates used for the analyses and the median follow-up duration will be reported (MFU also by trial & treatment group).

### 2.6.3.1 Subgroup Analyses and Covariate-adjusted HR Estimates

Same as first analysis.

### 2.6.3.2 Tables and Figures

Tables:

- AI Question (E+OFS vs T+OFS), stratified by cohort & nodal stratum
  - Primary treatment comparison: N events and patients, HR, 95% CI, log-rank test statistic and p-value, 8yr DFS, SE and 95% CI
  - By-trial (2) and by-cohort (4) treatment comparisons: N events and patients, HR, SE, 95% CI, 8yr DFS, SE and 95% CI

- Treatment effects within subgroups: N events and patients within each subgroup, treatment HR, 95% CI, 8yr DFS, SE and 95% CI
- Adjusted model: parameter estimate  $\pm$  SE, HR, 95% CI for each model covariate
- TEXT adjusted model (stratified by chemo & nodal strata): parameter estimate  $\pm$  SE, HR, 95% CI for each model covariate
- OFS Question (T+OFS vs T), stratified by chemo & nodal strata
  - Primary treatment comparison: N events and patients, HR, 95% CI, log-rank test statistic and p-value, 8yr DFS, SE and 95% CI
  - By-chemo cohort (2) treatment comparisons: N events and patients, HR, SE, 95% CI, 8yr DFS, SE and 95% CI
  - Treatment effects within subgroups: N events and patients within each subgroup, treatment HR, 95% CI, 8yr DFS, SE and 95% CI
- E+OFS vs T, stratified by chemo & nodal strata
  - Primary treatment comparison: N events and patients, HR, 95% CI, log-rank test statistic and p-value, 8yr DFS, SE and 95% CI
  - By-chemo cohort (2) treatment comparisons: N events and patients, HR, SE, 95% CI, 8yr DFS, SE and 95% CI
  - Treatment effects within subgroups: N events and patients within each subgroup, treatment HR, 95% CI, 8yr DFS, SE and 95% CI
- SOFT adjusted model (3-arms; stratified by chemo & nodal strata): parameter estimate  $\pm$  SE, HR, 95% CI for each model covariate; T as reference group for reporting T+OFS vs T and E+OFS vs T treatment comparisons

Figures:

- AI Question (E+OFS vs T+OFS)
  - KM plot of DFS, by treatment group, for entire analysis population (*y-axis: Percent Alive and Disease-Free; x-axis: Time since Randomization (yearly intervals); x-axis limited to 9 years (min SOFT/TEXT MFU plus 1 yr) and numbers at risk at yearly intervals*)
  - KM plots of DFS, by treatment group, for each trial, and for each of 4 cohorts
  - Forest plot of DFS, overall and for trials & for cohorts
  - Forest plot of DFS, overall and for subgroups

#### 2.6.4 Secondary efficacy analyses

Breast cancer-free interval, distant recurrence-free interval and overall survival will be summarized as described for DFS. Forest plots for BCFI; DRFI and OS depend on # events.

Sites of first treatment failure will be summarized overall and by treatment group, by trial & treatment group, and by cohort(or chemo strata) & treatment group as N (%).

Second (non-breast) malignancies as site of first failure, and deaths without prior cancer event will be summarized overall and by treatment group.

Tables:

- Primary treatment comparison for each of the 3 endpoints: N events and patients, HR, 95% CI, log-rank test statistic and p-value, 8yr DFS, SE and 95% CI

- Cohort treatment comparisons (4) for each of the 3 endpoints: N events and patients, HR, SE, 95% CI, 8yr DFS, SE and 95% CI
- Sites of first failure, overall and by treatment group
- Types of second non-breast malignancies, as site of first failure, overall and by treatment group.

Figures:

- KM plots of BCFI, by treatment group, for entire analysis population and for each of the 4 cohorts (*y-axis: Percent Free from Breast Cancer; x-axis*)
- KM plots of DRFI, by treatment group, for entire analysis population and for each of the 4 cohorts (*y-axis: Percent Free from Distant Recurrence*)
- KM plot of OS, by treatment group, for entire analysis population and for each of the 4 cohorts (*y-axis: Percent Alive*)

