2.2 Primary endpoint

2.2.1 Disease-free survival

2.3 Secondary endpoints

2.3.1 Overall survival

2.3.2 Systemic disease-free survival-Breast cancer-free interval and distant recurrencefree interval

- 2.3.3 Quality of life
- 2.3.4 Sites of first treatment failure
- 2.3.5 Late side effects of early menopause
- 2.3.6 Incidence of second (non-breast) malignancies
- 2.3.7 Causes of death without cancer event

3 Patient selection

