6.1 Trial end points

6.1.1 **Primary end point:** First confirmation of relapse (local, regional, or distant), contralateral breast cancer, second (non-breast) primary tumor, and/or death.

Disease-free survival (DFS) is defined as the time from randomization to local (including recurrence restricted to the breast after breast conserving treatment), regional or distant relapse, contralateral breast cancer, appearance of a second (non-breast) primary tumor, or death from any cause, whichever occurs first. Appearance of DCIS or LCIS either in the ipsilateral or in the contralateral breast will not be considered as an event for DFS (but must be reported on the Follow-Up Form). See Section 6.2.7 for other exceptions.

6.1.2 **Secondary end points:** Overall survival (OS) is defined as the time from randomization to death from any cause.

Systemic relapse is defined as any recurrent or metastatic disease in sites other than the local mastectomy scar/chest wall/skin, the ipsilateral breast in case of breast conservation, or the contralateral breast.

Systemic disease-free survival (SDFS) is defined as the time from randomization to systemic relapse, appearance of second (non-breast) primary tumor, or death, whichever occurs first. See Section 6.2.7 for exceptions.

Breast cancer-free interval (BCFI) is defined as the time from randomization to the earliest time of invasive breast recurrence (local, regional or distant relapse) or a new invasive breast cancer in the contralateral breast. Deaths without a prior breast cancer event are censored. The appearance of a second (non-breast) primary tumor is not considered as an event.

Distant recurrence-free interval (DRFI) is defined as the time from randomization to the earliest time of distant recurrence. Deaths without a prior breast cancer event are censored. The appearance of a second (non-breast) primary tumor is not considered as an event.

Quality of life. Sites of first treatment failure. Late side effects of early menopause. Incidence of second (non-breast) primaries. Causes of death without cancer event.

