9.2 Data analyses

The treatment comparisons for primary objectives will be based on disease-free survival (DFS: Section 6.0) using two-sided stratified logrank tests to determine if the treatment groups are different, with an overall experiment-wise alpha level equal to at most 0.05. Kaplan-Meier estimates of the DFS distributions will be calculated for each of the treatment arms. Cox proportional hazards regression models will be used to investigate whether the a treatment comparison is modified by adjustments for various covariates.

Other factors will be used to characterize the patients enrolled in the study and to provide descriptive statistics of outcomes according to subgroups of the population. These factors include age at randomization, type and schedule of initial chemotherapy, type of surgery, use of post mastectomy radiation, tumor size, tumor grade, hormone receptor proportion score, ER/PgR subgroup, use of trastuzumab, and Her2 subgroup. These analyses will be considered as secondary and descriptive.

The following additional secondary outcomes will be assessed: overall survival, breast cancer- free interval, distant recurrence-free interval, quality of life, sites of first recurrence, late side effects of early menopause, causes of death without recurrence, incidence of second (non-breast) malignancies.

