#### 2.1.2 Secondary Objectives

- Assess overall survival, breast cancer-free interval, and distant recurrence-free interval
- Assess quality of life (see separate analysis plan)
- Investigate sites of first treatment failure
- Assess late side effects of early menopause
- Assess the incidence of second (non-breast) malignancies and causes of death without cancer event
- TEXT: Investigate patient and tumor features that may contribute to inter-individual variability of responsiveness to GnRH analogue plus exemestane and GnRH analogue plus tamoxifen (see separate analysis plan)

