## 2.3 Endpoint Definitions

Endpoint definitions remain the same as in the first report.

Per IBCSG standard, the date of DFS event is the date a proven recurrence was first suspected. **Since the first trial report**, the 2425-RC Form SOP was clarified that in cases with multiple proven sites of first recurrence (within 2 months of each other), that the date first suspected should be the earliest of suspected dates from among those proven sites (which may not necessarily correspond to the site with the earliest proven date).

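### Incidence of second (non-breast) malignancies is a secondary endpoint with no stated first-event limit, but SAP 2.6.4 reports only those that are the first failure

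*SAP*

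**What the plan says.** The endpoint is named four times, each time without a first-event limit:

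- Protocol 2.3: "2.3.6 Incidence of second (non-breast) malignancies".
- Protocol 6.1.2: "Incidence of second (non-breast) primaries".
- Protocol 9.2, in the list of secondary outcomes: "causes of death without recurrence, incidence of second (non-breast) malignancies".
- SAP 2.1.2: "Assess the incidence of second (non-breast) malignancies and causes of death without cancer event".

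Each list also has a separate item for sites of first failure (first recurrence in Protocol 9.2). In SAP 2.1.2 it reads "Investigate sites of first treatment failure".

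The planned output is in SAP 2.6.4. The text says "Second (non-breast) malignancies as site of first failure, and deaths without prior cancer event will be summarized overall and by treatment group", and the table list says "Types of second non-breast malignancies, as site of first failure, overall and by treatment group". On definitions, SAP 2.3 says only "Endpoint definitions remain the same as in the first report".

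**The concern.** A patient who has a breast cancer event and later develops, say, a uterine cancer has a second (non-breast) malignancy. She is not counted in either output of SAP 2.6.4, because her first failure was the breast event. The second-malignancy table then only splits one row of the sites-of-first-failure table by type, and the separately listed incidence endpoint has no output of its own.

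At stake is the completeness of a descriptive endpoint with some safety meaning: Protocol 7.1, note K, gives uterine cancer as a risk of tamoxifen. No test or DFS estimate depends on it.

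**Working it through.** **1. The wording.** In these lists the documents add a qualifier where they want one: *first* for sites of failure, and *without cancer event* (Protocol 9.2: *without recurrence*) for causes of death. The incidence item has neither. SAP 2.6.4 adds a first-failure limit in both the text and the table list.

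**2. Other SAP output.** No other section plans a named summary of later second cancers. They are not on the targeted adverse event (AE) list (Protocol 7.1, note C). A few could appear as write-in AEs of grade 3 or higher (SAP 2.6.5.2), but only until 1 year after protocol treatment and tabulated by maximum grade. The SAP plans no SAE analysis.

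**3. Patients at risk of being missed.** Death from any cause either is a DFS event or follows one, so DFS events minus deaths gives patients alive after a DFS event. From SAP 1.3.3 this is 412 − 164 = 248 in SOFT and 285 − 101 = 184 in TEXT at the first analyses. Some of these had a second cancer as their first event. The documents do not say how many had a later one.

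**4. Size, under assumptions.** T is tamoxifen, E is exemestane.

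*From SAP 1.3.1 and 1.3.2:* 5-year DFS of 84.7% (T), 86.6% (T+OFS, SOFT), 87.3% (T+OFS, both trials) and 91.1% (E+OFS, both trials). With a constant hazard, h = −ln(S5)/5 gives 0.0332, 0.0288, 0.0272 and 0.0186 per year.

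*Assumed, not in the documents:* breast events are 85% of DFS events (range 75–90%), deaths without cancer 3%, second cancers the remaining 12% (22–7%). The second-cancer hazard is unchanged after a breast event. The death hazard after a breast event is μ = 0.165 per year (0.10–0.25); fitting 299 DFS events and 106 deaths in 2033 patients over 5.6 years gives 0.15 to 0.18. All patients are followed for 8 years, with equal arms.

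*Formulas:* let b = 0.85h, s = 0.12h and m = μ + s.

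- First-failure second cancers by 8 years: 0.12 × (1 − e^(−8h)).
- Person-years alive after a breast event and free of a second cancer, per patient: P = b/(m − h) × [(1 − e^(−8h))/h − (1 − e^(−8m))/m].
- Missed: s × P.

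*Worked for T:* b = 0.0282, s = 0.00399, m = 0.169. First-failure: 0.12 × 0.2333 = 28.0 per 1000. P = 0.2079 × (7.025 − 4.386) = 0.549. Missed: 0.00399 × 0.549 = 2.19 per 1000. Share missed: 2.19/(28.0 + 2.19) = 7.2%.

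| Arm | First failure per 1000 | Missed per 1000 (range) | Share missed (range) |
|---|---|---|---|
| T | 28.0 | 2.19 (1.14–4.07) | 7.2% (5.4–8.8%) |
| T+OFS, SOFT | 24.7 | 1.66 (0.87–3.10) | 6.3% (4.7–7.7%) |
| T+OFS, both trials | 23.4 | 1.49 (0.78–2.78) | 6.0% (4.5–7.3%) |
| E+OFS | 16.6 | 0.72 (0.38–1.34) | 4.2% (3.1–5.1%) |

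With no deaths after a breast event (μ = 0), the upper bounds are 11.0% (T), 9.7% (T+OFS, SOFT) and 6.4% (E+OFS).

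*Modelled counts:*

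- OFS Question, 2033 patients: 28.5 + 25.1 = 53.6 first-failure and 2.2 + 1.7 = 3.9 missed (2.0–7.3).
- AI Question, 4690 patients: 55.0 + 39.0 = 94.0 first-failure and 3.5 + 1.7 = 5.2 missed (2.7–9.7).

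*Between-arm distortion* is the ratio of the shares captured, if the true second-cancer risk is equal: about 1.010 for T+OFS against T, and 1.020 for E+OFS against T+OFS. With μ = 0 the maxima are 1.016 and 1.030.

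*Untested assumption:* the missed count scales almost in proportion to the second-cancer hazard after relapse. If that hazard doubled, T would miss about 4.4 per 1000, or 4.4/(28.0 + 4.4), roughly 13–14%.

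**The case against.** **The limit may be deliberate.** This is an update SAP. It carries definitions over from the first report and refers to an original SAP that was not supplied. The protocol never says whether incidence means first or any event. SAP 2.1.2 pairs it with deaths without a cancer event, and 2.6.4 gives both first-event wording, which can be read as specifying an open endpoint. The output is also correctly labelled. This stands as a reason for caution: the mismatch is shown only within the supplied documents. A correct label on a narrower output still leaves later cases unreported.

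**It is immaterial.** On the modelled first-failure counts, a 95% interval for the T+OFS to T ratio spans a factor of exp(1.96 × √(1/28.5 + 1/25.1)) = 1.71 either way, against a distortion of about 1%. This stands, and is why the point is minor.

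**Stronger readings that the documents do not support:**

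- A reader might infer that SAP 2.6.5.3 drops second primaries recorded on Form E. It names cardiovascular and cerebrovascular events, fractures and other severe AEs. Second primaries reach Form E as treatment failures (Protocol 6.2, 6.2.5), a separate route, and first-failure cases after treatment are still reported.
- A reader might infer that this reduction is hidden while others are declared. The others (2.6.5.3, 2.6.6.2, 2.6.7) are also stated only in their own sections, as this one is in 2.6.4.
- A reader might infer that many missed cases arose on trial therapy. Treatment could continue after a relapse in the conserved breast (Protocol 6.2.1.1), but SAP 2.6.6.2 treats protocol therapy as ended at any DFS event, and no document counts such patients.

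**Conclusion.** The point holds as a minor one. As written, the update leaves second cancers after an earlier breast event out of its incidence output, although the endpoint is named without that limit. Roughly 3 to 9% of second cancers would be missed, a few patients per comparison. These figures are modelled, not observed: they rest on an assumed event split and an unchanged second-cancer hazard after relapse, neither of which is in the documents. The absent original SAP leaves open whether the limit was intended. It would be wrong to infer that the primary results or the first-failure table are in error; both are unaffected.

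**What to change.** In SAP 2.6.4 add one descriptive table of all second (non-breast) malignancies from randomisation, regardless of earlier events, by arm and type (N and %). Take the cases from Form E and cross-check them with SAE reports. Keep the first-failure table as labelled. Footnote that ascertainment after distant relapse may be less complete.

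The SOFT sources exist: Form E runs yearly until death (Protocol 7.1), and second primaries are SAEs whether during or after treatment (7.3.2). The TEXT protocol was not supplied, so confirm its forms before including TEXT.

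The cost is one table and a small but new data cross-check. The Form E instruction sits in a section on treatment failure, so capture after relapse may be incomplete and the added count slightly low.

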## 2.6.5 Adverse Events / Safety

### 2.6.5.1 AE population

The AE population is the subset of patients in the ITT analysis population who started protocol treatment (and have at least 1 post-baseline AE form submitted). **This population will be updated from the first analysis using updated information, as necessary, and any such changes will be included in the report.**

### 2.6.5.2 AE analysis

Targeted AEs, and other grade 3-5 AEs, are collected on CRFs, until 1 year after the cessation of all protocol treatment. The grade and causality attribution are recorded according to the NCI Common Terminology Criteria for Adverse Events (CTCAE) version 3.0. In TEXT, chemotherapy-related AEs are collected separately.

The targeted AEs will be summarized by AE type and maximum grade over time, regardless of causality attribution. The maximum grade consolidates the reports of a given type of AE for a patient over time since randomization (i.e., baseline reports are excluded) by taking the maximum across time (i.e., a patient appears only once for a given type of AE). Patients with reports of multiple AEs of different types are reported multiple times under the relevant AE categories. Maximum grade 0 indicates that the AE type has not been reported.

Note, during a period of trial conduct, the IBCSG audit team was asking sites to record grade 3+ weight gain and obesity as other AEs; discussed among StatC/DMC/CC that CRFs record weight serially on E-form and any analysis of weight changes and/or obesity [in these or other IBCSG adjuvant trials] would use the actual weight, not the AE; as a result the audit team changed their practice. Therefore the weight change and obesity “other grade 3+” AEs will be deleted from dataset before summarizing other grade 3+ AEs because the incidence will not be interpretable.

Tables:

- AI Question (E+OFS vs T+OFS)
  - Targeted AEs reported according to treatment group (N; %)
  - Targeted AEs reported according to trial & treatment group (N;%)
  - Targeted AEs reported according to cohort & treatment group (N;%)

- Tables above repeated for the subset of events deemed possibly, probably or definitely related to study treatment(s)
- SOFT (E+OFS vs T+OFS vs T)
  - Targeted AEs reported according to treatment group (N; %)
  - Targeted AEs reported according to chemo strata & treatment group (N;%)
  - Tables above repeated for the subset of events deemed possibly, probably or definitely related to study treatment(s)

Other grade 3 or higher AEs are also requested on CRFs, by write-in text. All will be tabulated, similarly according to max grade, but the intention is to focus on those deemed possibly, probably or definitely related to study treatment(s), which will also be tabulated.

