8.1 Case report forms schedule—SOFT

The Data Management Manual for this trial contains instructions for submitting forms using the DataFax system.

RANDOMIZAT	TON FORMS	
Form IC	Informed Consent Form	Obtain before randomization and keep with patient records.
Forms 24QLC, 24-QLM, 24- QLS	QL Core and QL Module Forms; QL Supplement Form (for English-speaking Centers only).	DataFax baseline QL forms (see exceptions in Section 3.1.7). These forms are also required during follow-up (see instructions below).
Form 24-A	Confirmation of Registration Form	Fill in before contacting your Randomization Center or entering the IBCSG Registration/Randomization system to randomize. DataFax completed form for all patients randomized.
BASELINE FO	RMS	
Form 24-B	Clinical Form	DataFax within 1 month of randomization.
Form 24-C*	Surgery Form	DataFax within 1 month of randomization.
Form 24-H	Prior Treatment History Form	DataFax within 1 month of randomization.
Form 24-F*	Hormone Receptor Form	DataFax within 1 month of randomization with the hormone receptor report.
Form 24-P*	Pathology Form	DataFax within 1 month of randomization with a copy of the original pathology report.
Form 24-AE	Adverse Event Form	Complete prior to starting protocol treatment (tamoxifen, exemestane, OFS) and DataFax within 1 month of randomization. This form is also required at follow-up (see instructions below.)
Form 24-CCM	Concomitant Medications Form	Complete prior to starting protocol treatment (tamoxifen, exemestane, OFS) and DataFax within 1 month of randomization. This form is also required at follow-up (see instructions below.)
FOLLOW-UP F	FORMS	
Form 24-E	Follow-Up Form	DataFax every 3 months in Year 1, every 6 months during Years 2- 6, and yearly thereafter.
Form 24-OFS	Ovarian Function Suppression Form	DataFax at each follow-up period until completion of OFS.
Form 24-TE	Tamoxifen/Exemestane Form	DataFax at each follow-up period until the completion of tamoxifen and/or exemestane.
Form 24-AE	Adverse Event Form	DataFax at each follow-up period during protocol therapy (tamoxifen, exemestane, OFS), and with Form 24-E at 6 and 12 months after the last dose of protocol therapy. This form is also required at baseline.
Form 24-CCM	Concomitant Medications Form	DataFax at each follow-up period during protocol therapy (tamoxifen, exemestane, OFS), and with Form 24-E at 6 and 12 months after the last dose of protocol therapy. This form is also required at baseline.

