#### **1.3.2 OFS Question**

After a median follow-up of 67 months (5.6 years), DFS events were reported for 299 (14.7%) of 2033 patients in the ITT population. T+OFS non-significantly reduced hazard of a DFS event vs. T (HR=0.83; 95% CI, 0.66 to 1.04; P=0.10). The estimated 5-year DFS among patients assigned T+OFS was 86.6% (95% CI, 84.2% to 88.7%) versus 84.7% (95% CI, 82.2% to 86.9%) among patients assigned T. The relative effects of T+OFS vs. T were consistent between the two chemotherapy strata; as expected, the absolute difference at 5 years was more notable among patients who received prior chemotherapy. The reduction in hazard with T+OFS vs. T was consistently observed for the secondary endpoints of breast-cancer-free interval and distant recurrence-free interval. 106 (5.2%) deaths were reported, and on average there was a non-significantly reduced hazard of death; with all except 10 deaths among patients who received prior chemotherapy, the reduction in hazard was more apparent among this cohort of patients

At the time of the analysis, 26% of patients continued on protocol-assigned treatment. 31% and 24% of patients assigned to T+OFS and T have had grade 3-5 targeted AEs reported, of which hot flashes/flushes, musculoskeletal symptoms and hypertension were the most frequently reported.

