### 2.6.6.3 Tables and Figures

Tables:

- Treatment status, overall and by treatment group and trial and/or cohort

Figures:

- Cumulative incidence of early treatment discontinuation, by treatment group, and secondarily by cohort and/or trial and treatment group; without and with competing risk of DFS event that leads to treatment cessation.

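### Targeted AEs are compared as crude ever-reported percentages over a window set by each patient's own treatment duration, with no observation time shown by arm

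*SAP*

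**What the plan says.** SAP section 2.6.5.2 states that targeted AEs, and other AEs of grade 3 to 5, "are collected on CRFs, until 1 year after the cessation of all protocol treatment". Protocol section 8.1 agrees. The AE form is due as follows: "DataFax at each follow-up period during protocol therapy (tamoxifen, exemestane, OFS), and with Form 24-E at 6 and 12 months after the last dose". The clock starts when the last component stops, whether that is the oral drug or OFS.

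Reports since randomisation are then reduced to one value per patient and AE type by "taking the maximum across time (i.e., a patient appears only once for a given type of AE"). A type never reported counts as grade 0, however short the observation. The tables give N and % by arm: E+OFS v T+OFS for the AI Question and all three arms for SOFT. The AE population (2.6.5.1) requires that treatment was started and that one post-baseline AE form exists. It sets no minimum observation time.

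Nothing elsewhere evens out the windows. Section 2.6.5.3 leaves post-treatment AEs from the follow-up form out of the update. Section 2.6.6.3 plans a cumulative incidence, "without and with competing risk of DFS event that leads to treatment cessation", but only for early treatment discontinuation.

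For the first report, SAP section 1.3.2 states that "31% and 24% of patients assigned to T+OFS and T have had grade 3-5 targeted AEs reported".

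**The concern.** Treatment duration is a post-randomisation outcome and may itself depend on toxicity. A crude ever-percentage rises with time observed. If the arms are observed for different lengths of time, the percentages differ even when the AE rates do not.

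There are two routes:

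- **OFS Question.** A tamoxifen-alone patient leaves AE observation one year after stopping tamoxifen. A T+OFS patient who stops tamoxifen but continues OFS stays under observation. For the same oral stopping pattern the OFS window is equal or longer. If OFS patients stop everything sooner, it is shorter.
- **AI Question.** Both arms have two components, so the one-drug v two-drug route does not apply. Unequal early stopping still does: the arm that stops all treatment more often is watched for less time and can look safer.

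These tables are the SAP's between-arm comparison of harm, and the first-report differences are modest: 7 points in the OFS Question, and 1.2 points (30.6% v 29.4%, SAP section 1.3.1) in the AI Question.

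**Working it through.** **Inputs from the documents.** Oral drug and triptorelin are both planned to 5 years from randomisation (Protocol sections 5.1.1, 5.1.4 and 5.1.5). Adding 1 year gives a planned maximum AE window of about 6 years in every arm. The reported 31% and 24% come without counts or person-time, so there is no formula behind them to reproduce.

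**Assumptions (not in the documents).** AE hazard is constant and equal in all arms. A share p of patients stop the oral drug early, at a time uniform over 0-5 years. A share r of those keep OFS to 5 years, and the rest stop both together. The window is last stop + 1 year.

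**Formulas.** With hazard h:
- full window: F = 1 − exp(−6h)
- early stopper of everything: S = 1 − exp(−h)·[1 − exp(−5h)]/(5h)
- one component: F − p(F − S)
- OFS arm: F − p(1 − r)(F − S)
- spurious excess at equal p: p·r·(F − S)

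**Hazard of 24% over 5.5 years.** h = −ln(0.76)/5.5 = 0.0499. F = 25.87%, S = 15.81%, F − S = 10.07 points.

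| p | r | Excess in OFS arm (points) |
|---|---|---|
| 20% | 25% | 0.5 |
| 20% | 50% | 1.0 |
| 20% | 100% | 2.0 |
| 40% | 25% | 1.0 |
| 40% | 50% | 2.0 |
| 40% | 100% | 4.0 |

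**Sign reversal.** Take oral stopping of 20% (T) v 35% (T+OFS) with r = 25%. T = 25.87 − 0.20 × 10.07 = 23.9%. T+OFS = 25.87 − 0.35 × 0.75 × 10.07 = 23.2%. The OFS arm looks 0.6 points better.

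**Other stopping models.** These use exponential stopping, 10-50% per drug by 5 years, with T fixed at 24%:
- independent stop times: OFS arm 24.9% to 28.3%
- stop times correlated at 0.9: 24.3% to 25.3%
- AEs arising only in the first 2 years: at most 24.7%
- OFS patients stopping both drugs together and more often (25% v 40%): 22.3%

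**AI Question.** Suppose all treatment is stopped early in 15% v 35%, with equal hazard.
- At 24% over 5.5 years: 25.87 − 0.15 × 10.07 = 24.4%, against 25.87 − 0.35 × 10.07 = 22.3%.
- At an assumed 30% over 5.5 years: h = 0.0648, F = 32.23%, S = 19.96%, F − S = 12.28, giving 30.4% v 27.9%.

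**Could windows alone give 31% v 24%?** With an equal constant hazard, the OFS window would have to be ln(0.69)/ln(0.76) = 1.35 times the T window. If T averages 5.35 years (25% stopping), OFS needs 7.23 years, beyond the 6-year maximum. The largest ratio in the scenarios above is 1.20 (6.0 v 5.0 years at p = 40%, r = 100%). Conversely, if the OFS window were 1.12 or 1.20 times longer, the 1.35 hazard ratio implied by 31% v 24% would fall to 1.21 or 1.13.

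**The case against.** The planned windows are equal, no arm-level stopping or AE observation time is given, and by the update cut-off all patients should have ceased protocol treatment (SAP section 2.6.6.1). Protocol Table 7.1 also marks the AE form as mandatory at every visit to month 72 in all arms, without the on-treatment qualifier attached to the OFS and oral-drug forms. All this stands. The documents do not show that the arms were observed for different lengths of time. Protocol section 8.1 and the SAP, however, both tie AE collection to treatment, and nothing planned would reveal how the windows turned out.

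A reader might infer that OFS is bound to look worse, or that much of the 7-point gap is artefact. Neither follows. The direction depends on which arm stops all treatment sooner. The 4-point figure needs 40% early stopping with every stopper keeping OFS; at 25-50% retention the excess is 0.5 to 2 points.

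Toxicity in a patient who has stopped tamoxifen but continues OFS is also real harm of the regimen, and the working assumes the same hazard on and off treatment. An as-collected maximum-grade table is a usual descriptive summary, and no AE test is planned. That argues for keeping the tables, not for leaving out the observation time needed to read them.

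**Conclusion.** The point holds as a reporting weakness, not as a demonstrated bias. The planned AE measure depends on observation time, observation time depends on treatment duration, and the plan neither reports nor adjusts for it. Size and direction in this trial are unknown. Under an equal constant hazard and equal oral stopping, the spurious excess in the OFS arm is about 0.5 to 4 points, and less if stop times are correlated or AEs occur early. It reverses if OFS patients stop everything more often. In the AI Question the arm with more early stopping can look about 2 to 2.5 points safer at 15% v 35% stopping. That would matter beside a 1.2-point reported difference, but those stopping rates are assumed.

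This is a cheap improvement of low to moderate severity.

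**What to change.** In SAP section 2.6.5.2:

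1. Keep the maximum-grade N (%) tables.
2. Print patient-years of AE observation by arm beside them. State how the end of AE collection is set, including when OFS counts as ceased after oophorectomy or irradiation, and how the month-72 schedule in Protocol Table 7.1 fits with section 8.1.
3. For any targeted AE of grade 3 or higher, and for the main targeted types, add the cumulative incidence of first report by arm at fixed times from randomisation, for example 1, 3 and 5 years. Censor at the end of each patient's AE collection and treat death as a competing event.
4. As a sensitivity analysis, treat a DFS event as the competing event, in line with section 2.6.6.3.

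The cost is some programming on data already collected. Two limits should be stated. Onset is known only to the 3-6 month visit interval. Censoring at the end of collection may be informative, because collection ends when treatment stops, possibly for intolerance; the estimates are therefore descriptive. If the windows prove equal, the patient-years row will show it.
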